7.1.3 Other optional substudy parameters

- Systemic levels of biomarkers of lung injury
- Evaluation of regional ventilation distribution

7.2 Study procedures

Patients admitted to the participating centers' ICUs will be considered eligible if they fulfill the entry criteria. Eligible patients will be screened, their demographic criteria data recorded (registry: age, gender, type of oxygen support device), and those without exclusion criteria will be randomized. In total, 714 patients will be included.

Patient consent

According to local regulations, all patients or legal guardians must provide written informed consent before inclusion in the study. If patients cannot give informed consent due to the effects of acute illness, sedation, or hypoxemia, deferred consent will be obtained.

7.2.1 Randomization

Randomization procedure

Randomization will be performed using a dedicated website and will be balanced per center. *Randomization arms*

Central randomization with the use of a permutated-block randomization list (block length 6) will be used. Participants will be allocated to the prone position or standard care on a 1:1 ratio. At each site, at least two investigators will be involved: one who will be aware of the allocated intervention and collect the data; the other will remain blinded to the interventions and evaluate the outcomes.

7.2.2 Prone position

Supine to Prone

The patient will be placed in the prone position for at least 2 hours, which may be prolonged if the patient is comfortable or interrupted if the patient presents any criteria for prone position discontinuation (APPENDIX iii).

During the maneuver, FiO_2 will be increased by 25% above the baseline and then gradually decreased to the baseline value within the first 10 minutes of prone positioning, targeting for a SpO₂ of 94-96%. The total time of the prone position will be recorded.

The maneuver will be performed by two operators and the attending physician, while in patients with impaired mobility, up to 5 operators will be required. Skin protections will be used to avoid pressure sores. Also, the application of cushions will enhance patient tolerance to the

maneuver.

Arms can be at the side, in swimmer position, and can be moved to the patient's comfort. Vitals, SpO₂, and SpO₂/FiO₂ will be measured before and at the end of the prone position session.

Enteral or oral feeding will be interrupted 1 hour before prone positioning and re-established when the patient is in the semi-recumbent supine position.

Opiates, benzodiazepines, or alpha-2-adrenoceptor agonists can be used during the maneuvering at non-sedative doses to enable adaptation to the maneuver or treat anxiety symptoms related to respiratory failure.

If non-tolerance to the prone position, all clinical data will be collected, and the patients will be promptly rotated in the supine position. The reasons for prematurely unproning the patient will be accurately recorded. In case of sudden worsening of the oxygenation impairment or hemodynamics, 100% FiO₂ will be set, and the patient will be promptly positioned in the supine semi-recumbent position.

Prone to Supine

After the prone position period, the patient will be rotated to the semi-recumbent supine position for at least 2 hours and a maximum of 4 hours. This 2-hour time frame will depend on nursing availability, need for hygiene, complementary explorations, or diet.

As described previously, for the procedure, FiO_2 will be increased up to 25% above the baseline and then gradually decreased to the baseline value within the following 10 minutes targeting a SpO₂ of 94-96%.

Vitals, SpO_{2} , and SpO_{2}/FiO_{2} will be measured before and at the end of the supine position session.

Opiates, benzodiazepines, or alpha-2-adrenoceptor agonists can be used during maneuvering at non-sedative doses to enable adaptation to the maneuver or treat anxiety symptoms related to respiratory failure.

During the evening, the patient will be asked if the patient would prefer to remain supine or be rotated to prone according to the protocol.

If the patient remains hypoxemic, at clinician's criteria, the prone position could be continued more than 48 hours until respiratory failure improves.

7.2.3 Standard management

The standard management of patients with acute hypoxemic respiratory failure will be done according to the usual practices of each participating center.

7.2.4 Data to be collected

The documentation of the data will adhere to the timetable in APPENDIX v.

Pre-randomization variables

Pre-randomization variables will be collected:

- Gender and age; female + years
- Height and weight; kg + cm
- Date and time of hospital admission
- Source of admission to the ICU (emergency department, hospital ward, transfer from another ICU, transfer from a non-ICU ward of another hospital)
- Date and time of ICU admission
- Type of non-invasive respiratory support (HFNC, NIV, CPAP)
- COPD with inhalation therapy and/or steroids
- Smoking status; never, former (at least three months prior) or current
- History of active cancer; if yes, specify the type of cancer
- History of diabetes mellitus; oral medication or insulin therapy
- History of hypertension
- Use of angiotensin-converting enzyme inhibitor
- Use of angiotensin II receptor blocker
- Use of statins
- Actual organ function evaluation
 - Respiratory rate
 - SpO₂; %
 - SpO₂/FiO₂
 - ROX index; SpO₂/FiO₂: RR
 - Dyspnea defined according to Borg dyspnea scale
 - Chest X-ray

- Non-invasive mean arterial pressure; mmHg
- Heart rate; BPM
- Body temperature; °C
- BUN, Creatinine, AST, ALT, Bilirubin, Hemoglobin, Platelets, PTT, WBC count
- SOFA score
- APACHE II, SAPS II; any of those used by the participating center

Post-randomization variables

One hour before each position change (supine and prone), the following variables will be collected for the duration of the protocol, which will be for 48 hours (APPENDIX v):

- Organ function evaluation:
 - Respiratory rate
 - SpO₂; %
 - SpO₂/FiO₂
 - ROX index; SpO₂/FiO₂: RR
 - Dyspnea defined according to the Borg dyspnea scale (APPENDIX v)
 - Non-invasive mean arterial pressure; mmHg
 - Heart rate; BPM
- Non-invasive support device parameters:
 - HFNC: flow; liters/min. FiO₂; %
 - CPAP: PEEP; cmH₂O. Flow; liters/min; Tidal volume; ml. FiO₂; %
 - NIV: PEEP; cmH₂O. Pressure support over PEEP; cmH₂O. Flow; liters/min. Tidal volume; ml. FiO₂; %
- Complications possibly related to prone position:
 - New hypotension (BPsys < 90mmHg or BPsys drop > 10mmHg, if BPsys < 90 before the maneuver)
 - New bradycardia (HR <50bpm or HR drop > 20%, if HR < 50 before the maneuver)
 - New hypoxemia (SpO₂ ≤ 90% or SpO₂ drop > 5%, if SpO₂ < 90% before the maneuver)
 - Ulcers
 - Displacements of any of the following: respiratory support device, peripheral or venous central line, oro or nasogastric tube, urinary catheter

Post-protocol variables

The patients will be assessed daily between the third and the fourteenth day after the protocol and the last day before discharge from the ICU and the hospital. Discharge from critical care is defined as the first discharge to a medical or surgical ward in the hospital or another hospital; a transfer between ICUs is not considered a discharge from critical care. Hospital discharge is the first date that the patient is discharged to home/community; a transfer between hospitals is not considered as a hospital discharge. Clinical data and the presence of complications will be registered and the date of the development of any complication documented (see APPENDIX vi). The following variables will be collected:

- Continuation of prone position
- Continuation and time spent under the non-invasive respiratory support device
- Day and time of unassisted breathing; i.e., no ventilatory support and use of conventional supplemental oxygen or room air
- Chest X-ray
- Need for invasive mechanical ventilation
- Any need for anti-arrhythmic and vasoactive medication; if yes: specify
- Date of ICU discharge
- Date of hospital discharge

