7.1.2 Secondary study parameters/endpoints

- Effects on oxygenation defined by the SpO₂
- Days under the oxygen support device
- Total amount of time the patient remains in the prone position
- Related serious adverse events. The following will be considered serious adverse events:
 - Oxygen desaturations (SpO₂ <90%)
 - Episodes of hemodynamic instability (BPsys < 90mmHg or BPsys drop > 10mmHg if BPsys < 90 before the maneuver)
 - Need of orotracheal intubation
 - o Cardiac arrest
 - o Displacement of the non-invasive respiratory support device
 - o Removal of central venous line, if documented
 - o Displacement of an arterial line, if documented
 - o Displacement of a urinary catheter, if documented
- Respiratory rate
- Dyspnea defined according to the Borg dyspnea scale (APPENDIX iv)
- ICU-free days and hospital-free days at day 90
- Mortality at day 28 and day 90

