7.2.5 Blood samples (facultative)

At randomization and the end of the protocol (48 hours) in both groups (supine and prone), and for those centers that have the storage capacity, blood samples (2 x 5 ml in EDTA, citrate, and heparin) will be collected and stored at -80°C for measurement of markers of lung injury (angiopoietin-2, surfactant proteins D, RAGE). Blood samples will be sent and processed at a central laboratory.

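### The 48-hour readings are triggered by position changes, which only the prone arm has on schedule, so controls have no stated time for Borg dyspnea

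*Protocol*

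**What the plan says.** Section 7.1.2 lists respiratory rate and dyspnea among the secondary endpoints, the latter as "Dyspnea defined according to the Borg dyspnea scale (APPENDIX iv"), without an assessment time for either. Section 7.2.4 collects both before randomization in all patients. After randomization its timing rule is "One hour before each position change (supine and prone), the following variables will be collected for the duration of the protocol", with the protocol period set at 48 hours. The list under that rule includes respiratory rate, SpO2, SpO2/FiO2 and "Dyspnea defined according to the Borg dyspnea scale (APPENDIX v").

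Section 7.2.2 describes the turning cycle of the prone arm: at least 2 hours prone, with no stated maximum, then the "semi-recumbent supine position for at least 2 hours and a maximum of 4 hours". In the evening "the patient will be asked if the patient would prefer to remain supine" or be turned. Vital signs, SpO2 and SpO2/FiO2 are also read before and at the end of each prone session and each supine interval that follows. Under section 7.2.3, control care "will be done according to the usual practices of each participating center"; no turning schedule or measurement times are given.

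Appendix v has one mark each for *Respiratory variables* and *Hemodynamic variables* during the intervention, under the heading for randomized patients. On Days 1 to 7 it marks physical examination, SpO2 and adverse events, among others.

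**The concern.** The trial compares two arms, but the event that triggers the 48-hour readings belongs to the intervention in one of them. A site that follows section 7.2.4 to the letter records Borg scores around each turn in the prone arm and has no instruction on when to ask a control patient. Sites must then improvise or leave the item blank. Either way, the two arms' values are not matched in time.

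This matters most for Borg, because it is reported by the patient. Heart rate or SpO2 may be recoverable from a chart, but a dyspnea score that nobody asked for is not, and no analysis plan can restore it. The timing of data collection is a matter for the protocol, so this is not a detail that can be left to an analysis plan.

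**Working it through.** The protocol states no figure on this point, so there is none to reproduce. The check is a comparison of every place that sets a measurement time, followed by a count.

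**Post-randomization timing, by arm**

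| Source | Prone arm | Control arm |
|---|---|---|
| 7.2.4, 48-hour list (names Borg, respiratory rate, SpO2, SpO2/FiO2) | One hour before each turn | Trigger not scheduled |
| 7.2.2, session readings (vital signs, SpO2, SpO2/FiO2; Borg not named) | Before and at end of each session | Not applicable |
| Appendix v, *Respiratory variables* | Marked, no time | Marked, no time |
| Appendix v, Days 1–7 | SpO2 and physical examination daily | Same |
| 7.2.4, daily follow-up | Neither Borg nor respiratory rate listed | Same |

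The last row refers to the rule "The patients will be assessed daily between the third and the fourteenth day after the protocol". It does not fill the gap: it starts after the 48-hour window and its list omits both items.

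The parenthesis about supine and prone in the 7.2.4 rule could be read as naming the two arms, because section 7.2.5 uses the words that way: "At randomization and the end of the protocol (48 hours) in both groups (supine and prone"). There they follow a mention of groups; in 7.2.4 they follow a mention of position change. Even on the other reading, the trigger is still a position change, which controls do not have on schedule.

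**Turn-linked readings per prone patient in 48 hours**

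A cycle of P hours prone and S hours supine contains two turns, so turns = 2 × 48 / (P + S).

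- P = 2, S = 2 (both minima in 7.2.2): 2 × 48 / 4 = 24
- P = 2, S = 4 (supine maximum): 2 × 48 / 6 = 16
- P = 8, S = 4 (8 hours is an assumption): 2 × 48 / 12 = 8
- Two 8-hour nights spent supine (an assumption, based on the evening choice), leaving 48 − 16 = 32 hours of turning with P = 2: 2 × 32 / 6 = 10.7 to 2 × 32 / 4 = 16

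Longer prone sessions would give fewer than 8.

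**Controls in the same 48 hours**

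- Borg readings with a stated time: 0
- Respiratory-rate readings with a stated time, by name: 0
- SpO2 entries: 2 (Days 1 and 2, assuming days count from randomization)

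The zeros count stated times. They do not show that nothing would be measured.

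**Entries under common clock times**

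- Every 12 hours: 48 / 12 = 4 per patient, 714 × 4 = 2,856
- Every 6 hours: 48 / 6 = 8 per patient, 714 × 8 = 5,712

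**The case against.** The strongest reply is that controls are not outside the 48-hour collection. Section 7.2.4 defers to Appendix v for documentation, its list is headed as post-randomization without limit to one arm, and the Appendix v rows stand under randomized patients. That is right, and it rules out a reading that a reader might otherwise take from the trigger: that controls are not measured at all, or that Borg scores will certainly be missing. The documents support only that controls are probably included and their timing is left open.

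Respiratory rate is the weaker half of the point. It plainly belongs among respiratory variables and may be part of the daily physical examination, and patients are under close ICU monitoring.

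The reference to Appendix v after the Borg item might be taken to show that the timetable was meant to schedule Borg and fails to. More likely it is a wrong cross-reference: section 7.1.2 cites Appendix iv, which is the scale itself. The timetable uses grouped rows, so the absence of a Borg row proves little.

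Turn-linked readings also have a purpose of their own. Worsening dyspnea and falling SpO2 are criteria for stopping a prone session, and the complications list concerns events possibly related to proning. Those readings should stay.

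One might also infer that safety events are over-detected in the prone arm and that the safety comparison is biased. The documents do not allow that conclusion. ICU monitoring and the Appendix vi rule to record all adverse events, whatever their relation to the intervention, also capture events in controls.

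What remains is narrow: the one timing rule that names Borg uses a trigger that works in only one arm.

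**Conclusion.** The point holds as a limited design flaw. Section 7.2.4 states a rule that gives turn-linked Borg values in the prone arm (about 8 to 24 per patient in 48 hours, depending on session lengths partly assumed above) and no values at matched times in controls. The same applies to a lesser degree to respiratory rate and SpO2/FiO2, for which controls have only an untimed row. SpO2 is scheduled daily by name in both arms and is not missing.

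The consequence is confined to endpoints that section 8.2 treats as exploratory, since only the primary outcome is confirmatory. The rate of invasive mechanical ventilation and the sample size are unaffected. No bias size can be derived. The conclusion rests on reading the 7.2.4 trigger literally and on usual care having no scheduled turning. This is worth correcting because it is cheap; it is not a threat to the main result.

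**What to change.** In section 7.2.4 and Appendix v, set a few common clock times from randomization for both arms, for example every 12 hours to 48 hours, for Borg, respiratory rate, SpO2 and SpO2/FiO2, and base between-arm comparisons on these. Place the Borg question in waking hours, which speaks for 12-hourly rather than 6-hourly times. The protocol already uses this approach for the optional blood samples, taken at randomization and 48 hours in both groups.

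Keep the turn-linked readings and maneuver-related complications as description within the prone arm. Name Borg and respiratory rate in Appendix v with their times, and point the Borg item in 7.2.4 to Appendix iv.

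The cost is wording in two places and the CRF, plus about 4 entries per patient in both arms: up to 2,856 in total, or up to 5,712 if every 6 hours. The number is lower where a clock time coincides with a turn-linked reading. No extra patients or staff are needed.

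### With one first-discharge date each for ICU and hospital and no readmission dates, ICU-free days (and possibly hospital-free days) at day 90 would count time back in the unit as free

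*Protocol*

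**What the plan says.** Section 7.1.2 of the protocol names the secondary endpoint "ICU-free days and hospital-free days at day 90" and gives no formula for it.

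Section 7.2.4, under the post-protocol variables, defines the two discharge events:

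- ICU: "Discharge from critical care is defined as the first discharge to a medical or surgical ward in the hospital or another hospital", with the qualification that "a transfer between ICUs is not considered a discharge from critical care".
- Hospital: "Hospital discharge is the first date that the patient is discharged to home/community", with the qualification that "a transfer between hospitals is not considered as a hospital discharge".

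The list of variables in that section then has one entry for each: "Date of ICU discharge" and "Date of hospital discharge". Neither that list nor the timetable in Appendix v has an entry for an ICU or hospital readmission, or for the discharge that ends one.

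Follow-up in section 7.2.4 is described as "The patients will be assessed daily between the third and the fourteenth day after the protocol", plus the last day before ICU and hospital discharge. Appendix v also has a separate line for hospital-free days, marked at Day 28 and Day 90.

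**The concern.** A free-day count is meant to measure how much of the 90 days a patient spent alive and out of the unit. The protocol handles transfers explicitly, so a move between ICUs or between hospitals does not end the stay. It does not handle the patient who reaches a ward or goes home and then comes back.

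If ICU-free days are calculated from the listed dates, the clock stops at the first ward discharge and any later ICU stay is counted as free time. The patients affected are those who deteriorate after an apparent recovery. Two endpoints could then disagree about the same person: an intubation within 14 days enters the primary endpoint, while the ICU stay around it is absent from ICU-free days.

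This differs from a formula left to the SAP. An SAP can define free days as it wishes, but it cannot supply dates that the CRF did not ask for.

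**Working it through.** The protocol states no expected mean, standard deviation or readmission rate for free days, so there is no figure of its own to reproduce. The check has two parts: which data are available, and an illustration of size.

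**1. Can the listed data give a full 90-day count that includes readmissions?**

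| Source in the protocol | What it shows | What it does not show |
|---|---|---|
| 7.2.4, ICU and hospital discharge dates | End of the first stay | Any later stay |
| 7.2.4, daily assessment to day 14 | May show an early return to ICU or ventilation | End of a stay running past day 14; later readmissions |
| Appendix v, daily recovery status including ICU stay, Days 1 to 7 | Return to ICU in the first week | Anything after that week |
| Appendix vi, adverse events to day 90, with hospitalization or its prolongation meeting the SAE definition | A narrative may mention a readmission | Structured start and end dates |
| Appendix v, hospital-free days line at Day 28 and Day 90 | A value for hospital-free days | The rule by which the site counted it |

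For ICU-free days, the only complete 90-day count these items support is the one from first discharge. For hospital-free days a value is scheduled, but whether readmission days are subtracted depends on how each site reads section 7.2.4.

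**2. One patient (illustrative).** First ICU discharge on day 6, back in the ICU from day 9 to day 30, alive at day 90.

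- From first discharge: 90 − 6 = 84 ICU-free days.
- Counting all ICU time: days back = 30 − 9 = 21, so 84 − 21 = 63.

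The return on day 9 falls inside the daily window to day 14. The discharge on day 30 does not.

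**3. Shift in an arm's mean.** Let r be the share readmitted and L their mean days back before day 90, with death handled the same way under both counts. Then

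overstatement = r × L.

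Both inputs are assumptions. Two sets of values:

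- r = 3% to 15%, L = 3 to 14 days: 0.03 × 3 = 0.09 to 0.15 × 14 = 2.1 days.
- r = 5% to 10%, L = 10 to 30 days: 0.05 × 10 = 0.5 to 0.10 × 30 = 3 days.

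Together, roughly 0.1 to 3 days.

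**4. Shift in the between-arm difference.** With the same L in both arms,

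shift = (r in one arm − r in the other) × L.

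- Equal r: 0 days.
- 8% versus 5%: 0.03 × 3 = 0.09 to 0.03 × 14 = 0.42 days.
- 10% versus 5%: 0.05 × 3 = 0.15 to 0.05 × 14 = 0.7 days. With L = 30 it would be 0.05 × 30 = 1.5 days.

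The arm with more readmission is flattered. The protocol does not say which arm that would be.

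**The case against.** The strongest reply is that no sentence in the protocol ties free days to the discharge dates. Section 7.1.2 names the endpoint, section 7.2.4 defines discharge for data collection, and section 8.2 promises a separate SAP before data collection ends. The counting formula and the treatment of readmission belong naturally there. The first-discharge definition is also explicit, the same for both arms and careful about transfers. This stands as far as the formula goes: a reader might infer that the protocol builds free days on first discharge, but the text does not say so. It does not answer the data gap, because no SAP can recover dates that were not recorded.

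Second, Appendix v schedules hospital-free days as an item separate from the hospital discharge date. This weakens the hospital half considerably. What remains there is only the missing counting rule. The timetable as read ends in a stray mark just after that line, so a matching line for ICU-free days cannot be ruled out. Without a counting rule, it would leave the same question open.

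Third, readmissions are not invisible. Daily records and SAE reports will reveal some, particularly early ones. It would be wrong to say that nothing about them is captured, but these sources do not reliably give the end of a stay or late returns to the ICU.

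Two further readings are tempting and unsupported. One is that patients who relapse are scored as successes. Free days are a count with no success category; intubation to day 14 and death to days 28 and 90 are captured in their own endpoints, whatever the discharge date. The other is that the rule favours the prone arm. That requires proning to bring earlier discharge followed by relapse, which nothing in the protocol suggests; if proning reduced relapse, the rule would work against it.

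**Conclusion.** The point holds in a limited form. The protocol fixes each discharge as the first one, lists a single date for each, and asks for no readmission or re-discharge dates. ICU-free days derived from those dates would treat days back in the ICU as free, and hospital-free days would do the same wherever a site applied the first-discharge definition.

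Each arm's mean would be overstated by about 0.1 to 3 days. This rests entirely on assumed readmission shares (3% to 15%) and assumed days back (3 to 30), paired as shown in the working. The treatment difference is affected only if the readmission burden differs between arms, and the sign is unknown.

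Section 8.2 makes every analysis other than the primary exploratory. The primary endpoint, its sample size and the interim boundaries do not use discharge dates. This is a cheap improvement of minor severity, not an error that threatens the trial's main conclusion.

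**What to change.** Add one definition to section 7.1.2: ICU-free (hospital-free) days are the days from randomization to day 90 on which the patient is alive and outside any ICU (any hospital), with all readmission days subtracted.

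Add ICU readmission and re-discharge dates, and hospital readmission and re-discharge dates, to the CRF. Allow for more than one episode, and complete the fields at the Day 28 and Day 90 follow-up already in Appendix v. The first-discharge dates can stay as they are for describing the initial stay.

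The cost is one sentence, a few date fields and the extra data entry. There will be some recall error for readmissions to outside hospitals. The dates are easy to collect while follow-up is running and hard to reconstruct afterwards.
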